5.2. Exclusion Criteria

The following criteria should be checked at the time of study entry. The potential participant shall not be included in the study if any of exclusion criterion applies.

5.2.1. Medical Conditions

- 1. Pregnant or lactating female.
- 2. Female planning to become pregnant or planning to discontinue contraceptive precautions.
- 3. History of any reaction or hypersensitivity likely to be exacerbated by any component of the study intervention(s).
- 4. History or current diagnosis of autoimmune disease.
- 5. Any confirmed or suspected immunosuppressive or immunodeficient condition, based on medical history and physical examination (no laboratory testing required).
- 6. Hypersensitivity to latex.
- 7. Major congenital defects, as assessed by the investigator.
- 8. History of abnormal Papanicolaou test or abnormal cervical biopsy result.
- 9. History of external genital/vaginal warts.
- 10. History of positive HPV test.
- 11. Acute or chronic clinically significant pulmonary, cardiovascular, neurologic, hepatic or renal functional abnormality, as determined by physical examination or laboratory tests.
- 12. Any other clinical condition that, in the opinion of the investigator, might pose additional risk to the participant due to participation in the study.

Refer to Section 5.4 for criteria for the conditions for the temporary delay or enrollment and/or intervention.

5.2.2. Prior/Concomitant Therapy

- 13. Previous vaccination against HPV.
- 14. Previous exposure to monophosphoryl lipid A or AS04 adjuvant.
- 15. Use of any investigational or non-registered product (drug, vaccine or medical device) other than the study intervention(s) during the period beginning 30 days before the first dose of study intervention(s) (Day -29 to Day 1), or their planned use during the study period.
- 16. Planned administration/administration of a vaccine not foreseen by the study protocol in the period starting 30 days before each dose and ending 30 days after each dose of study interventions administration*
 - *In case emergency mass vaccination for an unforeseen public health threat (e.g., a pandemic) is organized by public health authorities outside the routine immunization program, the time period described above can be reduced if necessary for that vaccine, provided it is licensed and used according to its Product Information.
- 17. Administration of long-acting immune-modifying drugs at any time during the study period (e.g., infliximab).
- 18. Use of systemic cytotoxic agents within the previous 3 months prior to randomization into this study or at any time during the study period.
- 19. Chronic administration (defined as more than 14 days in total) of immunosuppressants or other immune-modifying drugs during the period starting 3 months prior to the first study

- intervention dose(s). For corticosteroids, this will mean prednisone equivalent \geq 20 mg/day for adult participants or \geq 0.5 mg/kg/day with maximum of 20 mg/day for participants under 18 years of age. Inhaled and topical steroids are allowed.
- 20. Administration of systemic immunoglobulins and/or any blood products or plasma derivatives during the period starting 3 months before the administration of the first dose of study interventions or planned administration during the study period.

5.2.3. Prior/Concurrent Clinical Study Experience

21. Concurrently participating in another clinical study, at any time during the study period, in which the participant has been or will be exposed to an investigational or a non-investigational intervention (drug/invasive medical device [see the definition in Glossary of Terms]).

5.2.4. Other Exclusions

- 22. History of /current chronic alcohol consumption and/or drug abuse.
- 23. Any study personnel or their immediate dependants, family, or household members.
- 24. Child in care.

5.2.5. Lifestyle Considerations

No restrictions pertaining to lifestyle and/or diet apply.

5.3. Screen Failures

Not applicable as there is no screening phase of the potential participants as part of this study.

5.4. Criteria for Temporary Delay for Enrollment and/or Intervention Administration

Enrollment and/or study intervention administration may be postponed within the permitted time interval until transient circumstances cited below are resolved and the participant stays eligible:

- Acute disease and/or fever at the time of enrollment and/or study intervention administration. Fever is defined as temperature ≥37.5°C/99.5°F. The preferred location for measuring temperature will be the axilla.
- Participants with a minor illness (such as mild diarrhea, mild upper respiratory infection) without fever may be enrolled and/or dosed at the discretion of the investigator.
- Use of antipyretics and/or analgesics and/or antibiotics within 3 days prior to study intervention administration.
- Participants with symptoms suggestive of active Coronavirus Disease 2019 (COVID-19) infection (e.g., fever, cough, etc.) until they are free of symptoms for at least 14 days.

• Enrollment and/or study intervention administration of participants with known COVID-19-positive contacts within the past 14 days should be delayed for at least 14 days since the exposure and if the participant remains free of symptoms.

6. STUDY INTERVENTIONS

6.1. Study Interventions Administered

The details on the vaccines administered in this study are provided in Table 6.

 Table 6
 Study Interventions Administered

Study vaccines	HPV9-High formulation	HPV9-Medium formulation	HPV9-Low formulation	Gardasil 9
Study vaccines formulation	GSKVx00000031357 (Dose Aa GSKVx000000031397); GSKVx000000031399 (Dose Ba GSKVx000000031400); GSKVx000000031402 (Dose Ca GSKVx000000031327); GSKVx000000031328 (Dose Da GSKVx000000031408); GSKVx000000031409 (Dose Ea GSKVx000000031407 (Dose Fa GSKVx000000031407 (Dose Fa GSKVx000000031407 (Dose Fa GSKVx000000031360); GSKVx000000031361 (Dose Ha GSKVx000000031361 (Dose Ha GSKVx000000031363 (Dose Ia GSKVx000000031363 (Dose Ia GSKVx000000031434); Excipients; Water for injections q.s. 0.5 mL	GSKVx000000031398 (Dose Ab GSKVx000000031397); GSKVx000000031382 (Dose Bb GSKVx000000031400); GSKVx0000000031403 (Dose Cb GSKVx000000031405 (Dose Db GSKVx000000031405 (Dose Db GSKVx000000031405 (Dose Eb GSKVx000000031410 (Dose Eb GSKVx000000031427); GSKVx0000000031428 (Dose Fb GSKVx000000031430 (Dose Gb GSKVx000000031430 (Dose Gb GSKVx000000031364); GSKVx000000031362 (Dose Hb GSKVx000000031371); GSKVx000000031433 (Dose Ib GSKVx000000031434); Excipients; Water for injections q.s. 0.5 mL	GSKVx000000031358 (Dose Ac GSKVx000000031397); GSKVx000000031401 (Dose Bc GSKVx000000031400); GSKVx000000031404 (Dose Cc GSKVx000000031406 (Dose Dc GSKVx000000031406 (Dose Dc GSKVx000000031426 (Dose Ec GSKVx000000031427); GSKVx000000031359 (Dose Fc GSKVx000000031359 (Dose Fc GSKVx000000031384); GSKVx000000031384); GSKVx000000031384); GSKVx000000031371); GSKVx000000031364 (Dose Ic GSKVx000000031364 (Dose Ic GSKVx000000031434); Excipients; Water for injections q.s. 0.5 mL	HPV6 L1 (30 μg) ¹ ; HPV11 L1 (40 μg) ¹ ; HPV16 L1 (60 μg) ¹ ; HPV18 L1 (40 μg) ¹ ; HPV31 L1 (20 μg) ¹ ; HPV33 L1 (20 μg) ¹ ; HPV45 L1 (20 μg) ¹ ; HPV52 L1 (20 μg) ¹ ; HPV58 L1 (20 μg) ¹ ; HPV58 L1 (20 μg) ¹ ; adsorbed on amorphous aluminum hydroxyphosphate sulfate; Amorphous aluminum hydroxyphosphate sulfate (0.5 mg Al ³⁺); Water for injections q.s. 0.5 mL
Dose form (Presentation)	Suspension for injection (syringe)	Suspension for injection (syringe)	Suspension for injection (syringe)	Suspension for injection (syringe)
Туре	Biologic/Combination Product	Biologic/Combination Product	Biologic/Combination Product	Biologic/Combination Product
Route of administration	Intramuscular	Intramuscular	Intramuscular	Intramuscular
Location	Deltoid	Deltoid	Deltoid	Deltoid
Directionality	Upper	Upper	Upper	Upper
Laterality*	Nondominant	Nondominant	Nondominant	Nondominant
Number of doses to be administered	3	3	3	3
Volume to be administered	0.5 mL	0.5 mL	0.5 mL	0.5 mL
Packaging, labeling and trademark	Refer to the Study Reference Manual for details	Refer to the Study Reference Manual for details	Refer to the Study Reference Manual for details	Refer to the Study Reference Manual for details
Manufacturer	GlaxoSmithKline Biologicals SA (GSK)	GSK	GSK	Merck & Co.

^{*}The nondominant arm is the preferred arm of injection. In case it is not possible to administer the vaccine in the nondominant arm, an injection in the dominant arm may be performed.

6.2. Preparation/Handling/Storage/Accountability

The study vaccines must be stored at the respective label storage temperature conditions in a safe and locked place. Access to the storage space should be limited to authorized study personnel. The storage conditions will be assessed during pre-study activities under the responsibility of IQVIA. The storage temperature should be continuously monitored with calibrated (if not validated) temperature monitoring device(s) and recorded. Refer to the Study Reference Manual (SRM)/pharmacy manual for more details on storage of the study intervention(s).

6.3. Measures to Minimize Bias: Randomization and Blinding

6.3.1. Participant Identification

Participant identification numbers (IDs) will be assigned sequentially to the participants who have consented or provided assent with consent from each participant's parent(s)/LAR(s) to participate in the study, according to the range of participant IDs allocated to each study center. The participant IDs will be documented in the electronic Case Report Form (eCRF).

The eligibility of the participant will be determined based on the inclusion and exclusion criteria listed in Section 5. The participant ID will be the participant's unique identification number for all eCRFs and associated study documentation that will be used for duration of the study. If the participant is terminated from the study, her participant ID cannot be re-assigned.

6.3.2. Randomization to Study Intervention

All eligible participants will be centrally randomized to the study group at a 1:1:1:1 ratio using Interactive Voice Response System (IVRS)/Interactive Web Response System (IWRS) randomization (refer to Glossary of Terms for a definition of IVRS/IWRS). At study initiation, log in information and directions for the IVRS will be provided to each study center. The study and the center will be used as a minimization factor for randomization in Step 1 and the study, the center and will be used as a minimization factor for randomization in Step 2.

The participants will receive a unique treatment number (refer to Glossary of Terms for a definition of a treatment number). Once a treatment number has been assigned, it cannot be re-assigned.

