9.2.2.1. Exploratory Immunologic Non-Inferiority Analyses

Exploratory immunologic non-inferiority analyses will be performed in the study, to help in decision making of the formulation selection for phase 3 (Table 18).

The estimated sample size of 216 evaluable participants in each group provides at least 94% power to evaluate non-inferiority of a formulation in terms of antibody geometric mean concentrations (GMCs) measured by the electrochemiluminescence (ECL) assay.

In order to control the global type I error to below 7.5%, Bonferroni correction will be applied. The non-inferiority of each of the investigational formulations will be assessed at 2.5% type I error. That is, the non-inferiority in terms of antibody GMC for the investigational formulation will be reached, if the lower limit of the 2-sided 95% CI for the antibody GMC ratio (investigational group/*Gardasil 9* group) is not less than 0.5 for each of the 9 HPV types. To account for the multiplicity of comparison for 9 HPV types, the global type II errors are conservatively estimated as the sum of individual type II errors.

Table 18 Power to Show That the Lower Limit of the 2-sided 95% CI on Anti-HPV IgG Antibody GMC ratio (HPV-9 Vaccine Group Divided by *Gardasil 9* Group), 1 Month After Dose 3 is Not Less Than 0.5

Standard deviation (Log ₁₀ [concentration])	N evaluable (in each group)	Type II error for each HPV type	Overall Power
0.7	216	0.6%	94.6%

CI = confidence interval; GMC = geometric mean concentration; HPV = human papillomavirus virus; IgG = immunoglobulin G

Power was obtained using PASS 2019, non-inferiority test for 2 means, under the alternative of equal means and variances.

Since there are no immunogenicity data generated with the assay that will be used in this study, several studies with various multivalent HPV formulations in the age group 16-26 years were reviewed and a conservative standard deviation for log₁₀ transformed antibody concentrations of 0.7 for each of the 9 HPV types is used for the computation of power.

If the standard deviation for \log_{10} transformed antibody concentrations is ≤ 0.47 , the sample size of 216 evaluable participants in each group provides at least 73% power to assess the non-inferiority of a formulation in terms of antibody GMCs with a non-inferiority margin of 0.67.

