9.4.2.2.1. Within Groups Assessment

For each group at each time point for which a blood sample result is available, the following analyses will be conducted:

- Seroconversion and seropositivity rates for each antigen (with exact 95% CI) will be calculated.
 - Seroconversion is defined as the appearance of antibodies (i.e., concentrations/titer greater than or equal to the cut-off value) in the serum of participants seronegative before vaccination.
- Antibody GMCs/GMTs with 95% CI and range of antibody concentrations/titers will be tabulated for each antigen.

- The antibody GMCs will be derived considering log-transformed concentrations are normally distributed with unknown variance. Concentration below the assay cut-off will be assigned half the cut-off for the purpose of antibody GMC computation.
- The distribution of antibody concentrations/titers for each antigen will be displayed using reverse cumulative curves for the sub-cohort of initially seronegative participants.
- Pearson coefficient of correlation between anti-HPV IgG antibody concentration and anti-HPV neutralizing antibody titers with associated P-value will be calculated for each investigational adjuvanted vaccines group and *Gardasil 9* group for each antigen for timepoint and overall. The Pearson correlation coefficient is computed by log₁₀ transformation of specific antibody concentrations. Scatter plots will be generated.
- For each HPV type, the functional relationship between the pair of assay methods (pseudovirion-based neutralization assay [PBNA] versus ECL) will be estimated by timepoint using the Deming's regression model (Brown et al, 2014).

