9.4.2.2.2. Exploratory Between Group Assessment

For each HPV antigen, antibody GMC ratios and the 2-sided 95% CIs of antibody GMC ratios will be computed using an analysis of variance model on the log10 transformation of the antibody concentration adjusted for country effect. This analysis will be performed at Month 3 (1-month post-dose 2) and at Month 7 (1-month post-dose 3) time points. The non-inferiority of different vaccine formulations to the control group will be assessed if the lower limit of the 2-sided 95% CI is not less than the defined non-inferiority limit.

Additional exploratory group comparisons may be performed to facilitate the formulation selection.

9.4.3. iSRC Analyses

The analysis will be based on the ES. The analyses will be further described in detail in the statistical analysis plan.

- Demographic characteristics, baseline general medical and vaccination history, withdrawals from the study.
- Study intervention exposure by group and by intervention.
- Summary tables containing information on any events considered in the holding rules and other events (SAE, any withdrawal due to intervention-related AE, any AEs causing withdrawal from the study).
- Incidence of solicited administration site AEs (pain, redness, swelling): any grade, Grade 3 (2-days or more after Dose 1, 7-day follow-up period after intervention), any solicited administration site AEs leading to hospitalization within 7 days (Day 1 Day 7) after each vaccine dose.

- Incidence of solicited systemic AEs (fever, headache, fatigue, myalgia, and arthralgia): any grade, Grade 3, any related, Grade 3 related (2-days or more after Dose 1, 7-day follow-up period after each intervention), any solicited systemic AEs leading to hospitalization, fever >40°C (104°F), within 7 days (Day 1 Day 7) after each vaccine dose).
- Incidence of unsolicited AEs: any, Grade 3, any related, Grade 3 related (7-day and 30-day follow-up period after each intervention).
- Any, Grade 3 or above abnormality in pre-specified hematology and biochemistry parameters with an event onset within 7 days (Day 1 Day 7) after each vaccine dose.
- Incidence of SAEs: Any, any related, fatal, fatal related.
- Incidence of pIMDs: Any, any related.
- Any medically attended events.
- Any pregnancy and pregnancy outcomes, overall and pregnancy exposures (i.e., exposures during pregnancy).

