8. STATISTICAL CONSIDERATIONS

8.1. Adjustments for Covariates and Factors to be Included in Analyses

For details on the factors to be used in the analysis refer to section 17.1 and 17.2. The model will include all groups and country as fixed categorical effects in the ANOVA model.

Document: \\quintiles.net\Enterprise\Apps\sasdata\SAS\\SAS\GlaxoSmithKline\HPV\213749

(HPV9)\Biostatistics\Documentation\SAP\GSK_213749(HPV9-AS04-

001)_WZA97329_SAP_Final_v3.0_02FEB2024.docx

Author: PPD Version Number: 3.0

Version Date: 02FEB2024

Template No.: CS_TP_BS016 Revision 7 Reference: CS_WI_BS005

Page 30 of 48

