16.2.4. Exploratory Immunogenicity Variables

The exploratory immunogenicity analyses will be performed for the Month 3 and Month 7 PPS.

16.2.4.1. ANTI-HPV IGG ANTIBODY CONCENTRATION BETWEEN GROUP ASSESSMENT Anti-HPV IgG antibody concentration at Month 3 and Month 7 for each antigen.

For each antigen an adjusted GMC and GMC ratio with 2-sided 95% CI for intervention group which is derived from an ANOVA model on log10 transformed concentration will be tabulated for anti-HPV IgG antibody concentration adjusted for country effect. The analysis will be performed at Month 3 and at Month 7, summarised for the pre-vaccination status of seronegative, seropositive and total. The model will be based on the data from all groups, will include study group and country as a fixed effect and will be based on the PPS. The non-inferiority of different vaccine formulations to the control group will be assessed if the lower limit of the 2-sided 95% CI is not less than the defined non-inferiority limit. The non-inferiority between different vaccine formulations will also be assessed.

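### Center is a minimization factor in both steps, but the exploratory GMC and GMT ratio models adjust only for country, so their intervals are mildly conservative to the extent that centers differ within country

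*Protocol*

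**What the plan says.** Protocol 6.3.2 sets a central 1:1:1:1 allocation and names center among the minimization factors in each step. For Step 1: "The study and the center will be used as a minimization factor for randomization in Step 1". For Step 2: "the study, the center and will be used as a minimization factor for randomization in Step 2". A further Step 2 factor is blank in the public text.

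The between-group models do not carry center forward. Protocol 9.4.2.2.2 specifies an "analysis of variance model on the log10 transformation of the antibody concentration adjusted for country effect". SAP 8.1 repeats this: "The model will include all groups and country as fixed categorical effects in the ANOVA model". SAP 16.2.4.1 (IgG GMC ratios) and 16.2.4.3 (neutralizing GMT ratios) each say that the model "will include study group and country as a fixed effect and will be based on the PPS".

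SAP 8.2, on multicenter studies, does not mention center effects. The sensitivity analyses in SAP 16.4 concern values above the upper limit of quantification. No analysis with center is planned.

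**The concern.** Balancing groups on a factor that predicts the outcome removes that factor's contribution to the true variance of the group difference. If the factor is then left out of the model, its variance stays in the residual mean square and the reported standard error is too large. Country absorbs the differences between countries. What remains is variation between centers within a country.

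The affected quantities are the ratio intervals against Gardasil 9 and between formulations. They are exploratory, but Protocol 9.1 and 9.2.2.1 give them a purpose: helping to choose the formulation for phase 3. A formulation must meet the margin for all nine HPV types, so a small loss per type adds up over nine comparisons.

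**Working it through.** **Inputs.** From Protocol 9.2.2.1: 216 evaluable per group, log10 SD 0.7, margin 0.5, true ratio 1, two-sided 95% interval, type II errors summed over nine types. The same section gives a conditional scenario with margin 0.67 and SD 0.47. The within-country center share of variance, *v*, is in neither document; neither is the number of centers. I assume *v* = 0, 2%, 5% and 10%, and treat the planning SD as the SD left after country.

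**Step 1: the plan's own figures.** The standard error of the log10 difference is 0.7 × √(2/216) = 0.0674, and the margin is log10(2) = 0.301. By normal approximation, per-type power is 99.39% (type II error 0.605%) and overall power is 1 − 9 × 0.00605 = 94.55%. Noncentral t gives 0.622% and 94.40%. Table 18 states 0.6% and 94.6%, so the figure reproduces without any center term. At margin 0.67 and SD 0.47, overall power is 73.3% (normal) or 72.8% (t), against a stated 73% or more.

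**Step 2: effect of fitting center, with exact balance within center.** The SD falls from σ to σ√(1 − *v*).

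- Interval width, center-adjusted relative to country-only: √(1 − *v*).
- Half-width on log10 at SD 0.7: 1.96 × 0.0674 × √(1 − *v*). The lower limit at an observed ratio of 1 is 10 to the minus half-width.
- True coverage of the country-only interval: 2Φ(1.96/√(1 − *v*)) − 1.
- Power: as in Step 1 (noncentral t) with the reduced SD.

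| Assumed *v* | Width ratio | Half-width | Lower limit at ratio 1 | Country-only coverage | Power, margin 0.5 | Power, margin 0.67 |
|---|---|---|---|---|---|---|
| 0% | 1.000 | 0.1320 | 0.738 | 95.0% | 94.4% | 72.8% |
| 2% | 0.990 | 0.1307 | 0.740 | 95.2% | 95.1% | 75.1% |
| 5% | 0.975 | 0.1287 | 0.744 | 95.6% | 96.0% | 78.4% |
| 10% | 0.949 | 0.1252 | 0.749 | 96.1% | 97.2% | 83.3% |

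A simulation with 864 participants, four arms balanced within center, four countries and 24 or 72 centers gave width ratios of 1.000, 0.990–0.992, 0.976–0.978 and 0.951–0.956 for the four shares. This agrees with the formula.

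**Step 3: why these are upper bounds.** Minimization balances enrolment, whereas the models run on the per-protocol set. If a fraction *q* of each center is retained at random, the true variance of the difference is about (1 − *vq*) times what the country-only model reports, so the standard error is overstated by 1/√(1 − *vq*).

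- IgG, 20% non-evaluable (*q* = 0.8), *v* = 10%: 1/√0.92 = 1.043, about 4% rather than 5.4%.
- Month 7 neutralization, 120 evaluable of 270 (*q* = 0.44), *v* = 10%: 1/√0.956 = 1.023, about 2%. Protocol 6.3.4 gives no rule for choosing the subset, so random selection is an assumption.

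Simulation at *v* = 10% with 80% retained still gave intervals about 4% narrower with center fitted.

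**The case against.** The strongest case against is that the loss is hypothetical. No between-center variance is reported. IgG testing is at one sponsor laboratory and neutralization testing is also centralized (Protocol 8.1.2 and Appendix 3), so local assay differences, a usual source of center effects, are absent. Country already removes the coarser part. The comparisons are exploratory and the error is on the safe side. This all stands, and it is why the point is conditional and small.

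The margin 0.67 column also looks more dramatic than it is. By normal approximation, per-type power at a 10% share rises only from 97.0% to 98.2%; summing type II errors over nine types turns this into about ten points. That scenario is conditional on an SD of 0.47 or less, while the margin that defines success is 0.5.

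A mixed model is not free of trouble either. Nine types, two timepoints, three serostatus strata and two assays make 9 × 2 × 3 × 2 = 108 fits, before sensitivity reruns, and some seropositive strata may be small. That calls for a fallback rule but does not justify leaving center out.

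A reader might infer that the match between design and model fails further because of the unnamed Step 2 factor. The documents do not support this: the name is blank in the public text, so it cannot be checked and is no fault of the plan.

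**Conclusion.** The mismatch is explicit, and the direction is clear: leaving out a balanced factor can only make the ratio intervals conservative. The size depends on a variance share that the documents do not give. For assumed shares of 0% to 10%, fitting center would narrow the intervals by at most 0% to about 5%, and by less in the per-protocol set and the Month 7 neutralization subset.

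Three stronger readings are tempting, and the documents do not support them:

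- **The intervals are definitely too wide.** At a zero within-country center share the widths are equal.
- **The trial is underpowered or its type I error is wrong.** The stated power reproduces with no gain from center, and fitting center could only raise it. The plan says "The non-inferiority of each of the investigational formulations will be assessed at 2.5% type I error"; under the country-only model the true error is at or below that level.
- **The primary immunogenicity result is affected.** The Month 7 GMC intervals are within-group: "The antibody GMCs will be derived considering log-transformed concentrations are normally distributed with unknown variance". Neither Protocol 9.4.1.2.1 nor SAP 16.1.3 names a country or center term for them.

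This is a worthwhile refinement of low severity.

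**What to change.** In SAP 8.1, 16.2.4.1 and 16.2.4.3, keep study group and country as fixed effects and add center nested in country as a random intercept, which copes with small centers. State in advance that an analysis reverts to the country-only model if the center variance is estimated as zero or the fit does not converge, for example in a small seropositive stratum. List the change in SAP 4.3, because Protocol 9.4.2.2.2 names country only. If the sponsor prefers country alone, SAP 8.2 should give the reason, and a center-adjusted sensitivity analysis should be added.

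While editing SAP 8.1, correct its cross-reference: it points to sections 17.1 and 17.2, which cover safety, for the model factors, whereas the ANOVA models are in 16.2.4.

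The cost is a mixed model in place of ANOVA and one fallback rule to program and report. No new data are needed.
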